3. Research Plan

We will prospectively enroll 60 adult patients with 1-3 brain metastases who are eligible for treatment with intracranial stereotactic radiosurgery (SRS) at UC San Diego(UCSD)/Moore's Cancer Center.

Inclusion criteria include: age ≥ 18 ; Eastern Cooperative Oncology Group (ECOG) performance status of 0-2 (score of 0, no symptoms; 1, mild symptoms; 2, symptomatic, $< 50\%$ in bed during the day); pathologic confirmation of extra-cerebral tumor site (i.e. breast, lung, melanoma); ability to answer questions and follow commands via neurocognitive testing; estimated life expectancy > 6 months.

Exclusion criteria include: inability to undergo MRI with contrast, prior WBRT, ineligibility for brain SRS (i.e. leptomeningeal metastases; metastases from lung small cell carcinoma or primary CNS lymphoma), ineligibility for cognitive-sparing (tumor infiltrating hippocampus or critical white matter (WM) tracts). Concurrent chemotherapy with brain SRS is not allowed on study. These criteria closely follow the Alliance Trial N0574⁵, given that the cognitive deterioration rate from their standard SRS arm will be used as historical controls to power the current trial. Patient and tumor-specific variables including age, sex, race/ethnicity, educational status, occupation, primary tumor histology, systemic therapy, use of steroids and anti-epileptic drugs, tumor number, tumor size and tumor location, will be prospectively recorded.

The study protocol and timeline for each patient is shown in Figure 1 below. Patients will undergo MR imaging with DTI and 3D volumetric imaging at baseline (pre-SRS), and 1 month, 3 months, and 6 months afterwards. This regimen of post-SRS MR imaging is clinical standard of care². Segmentation of critical white matter and hippocampal volumes will be performed pre-SRS for use in brain SRS planning. Formal neurocognitive assessments will be performed at baseline and 3 months post-SRS⁵.

[figure not shown]

Figure 1. Timeline of consent, MRIs, Neurocognitive (NC) assessments, SRS planning and Delivery, and Follow-ups. WM=White matter; HC=Hippocampus.

Recruitment

Subjects will include those patients seen at UC San Diego/Moore's Cancer Center. A study coordinator will screen for eligible adult patients with brain metastases. They will review the patient's medical record and determine if they would be a candidate for the study. The principal investigator will be notified of subject eligibility and consult

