with the treating radiation oncologist as to whether the patient is eligible. Study investigator(s) will approach the subject and offer participation in the trial. Subjects willing to participate will sign informed consent, approved by the UC San Diego Institutional Review Board. Approximately 150 patients are treated at UCSD yearly that meet our eligibility criteria.

Inclusion Criteria

1. Patients 18 years or older
2. One to three brain metastases targets, all smaller than 3 cm in diameter (intact or resected tumor bed)
3. Eastern cooperative Oncology Group (ECOG) performance status 0-2 (score of 0, no symptoms; 1, mild symptoms; 2, symptomatic, <50% in bed during the day)
4. Ability to answer questions and follow commands via neurocognitive testing
5. Estimated life expectancy greater than 6 months
6. Pathologic confirmation of extracerebral tumor site (eg, lung, breast, prostate) from either the primary site or a metastatic lesion
7. Willingness/Ability to undergo brain MRI scans
8. Able to give informed consent

Exclusion Criteria

1. Pregnant or nursing women
2. Women of childbearing potential unwilling to use adequate contraception
3. Inability to complete a magnetic resonance imaging scan with contrast
4. Tumor directly invading the critical area to be spared (for example a patient with tumor invading a critical white matter tract; ineligible for cognitive-sparing)
5. Planned chemotherapy during SRS (on the day of SRS)
6. Previous whole brain radiation therapy
7. Leptomeningeal metastases (ineligible for SRS)
8. Metastases from primary germ cell tumor, small cell carcinoma, or primary CNS lymphoma (ineligible for SRS)

Screening Evaluation

Evaluation includes standard studies for brain metastases which may include but are not limited to: appropriate blood work including CBC and a complete metabolic panel and brain MRI. Previous biopsy results and medical history are necessary to evaluate disease status. There are no study-related screening procedures other than the informed consent process.

Informed Consent

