Patients will be seen by the treating physician on the day of SRS, and on subsequent follow-up visits. They will be followed closely with clinical and imaging exams for safety and tumor recurrence (i.e., 1 month, 3 months, 6 months post-SRS). All treatment-related toxic effects and adverse events will be recorded according to NCI Common Terminology Criteria for Adverse Events, version 4.0. Local tumor control rates for each treated lesion will be assessed according to the revised Response Assessment in Neuro-oncology (RANO) criteria^{81,82}.

Payment

Parking for study patients related to study visits will be complementary. Subjects will be compensated \$100 for participation in this study to help compensate for time and travel costs.

Statistical Considerations

Primary Objective Analysis:

Cognitive test results (pre- and post-SRS) will be scored based on standardized published norms^{72,87}. Cognitive deterioration will be defined as a decline of greater than 1 SD on at least 1 of the 7 cognitive tests (Table 2, not including BDI or FACT-BR). Fisher's exact 2-group binomial test will be used to compare the proportion of patients with 3-month post-SRS cognitive deterioration between the current cognitive-sparing SRS study and previously reported with standard SRS.⁵ Further analyses of pre- to post-SRS cognitive change for each test will

utilize a reliable change index (RCI)⁸⁷. This index is derived from the standard error of measurement of each test, and it represents the 90% confidence interval (CI) for the difference in raw scores from baseline to follow-up that is expected if no real change has occurred. RCI values below the 90% CI are indicative of significant decline. RCIs also account for practice effects, which is ideal for this study where evaluations are 3 months apart. One-sample t-tests ($H_0=0$) will be used to determine significant group decline in RCIs by test and cognitive domain. Pearson correlation coefficients will be used to assess associations between RCIs and depression scores. Bonferroni corrections will be applied to control for Type I errors due to multiple comparisons.

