With RCI at 3-months post-SRS as the outcome variable, linear regression modeling will be used to analyze patient-specific (e.g. age, sex), tumor-specific (e.g. histology, number of lesions, imaging progression), and treatment-specific (e.g. previous chemotherapy, anti-epileptic drugs) predictors of neurocognitive change after cognitive-sparing SRS. Model selection will be based on Akaike Information Criterion (AIC)^{88,89}. Given the small sample size and multiple variables of interest, this will be an exploratory analysis. Given that cognitive-sparing on this study will not be performed at the sacrifice of tumor coverage, we expect the overall local control and survival rates in the cohort to be comparable to those in other studies of SRS alone for patients with 1-3 brain metastases^{1,5,6,22}. Treated tumor local control rates will be assessed at 3- and 6-months post-SRS. Local tumor control of each treated lesion will be assessed with modified RANO criteria⁸⁴ where tumor progression is defined as >25% increase in the size of a treated lesion. Tumor progression of treated metastases will be evaluated independently of the development of new lesions⁵. Local tumor control rate at 6 months and overall survival rate (death from any cause) at 12 months will be compared to historical values⁵ using a 1-sample t-test.

Secondary Objective Analyses

The imaging biomarker of each structure (mean white matter diffusivity metrics and hippocampal volume) will be modeled as a function of time using linear mixed effect models^{13,16}. These models are well-suited for longitudinal analysis since they account for within-subject correlation between repeated measures, and allow for incomplete outcome data. Individual structures will be classified based on whether they received greater or less than the median dose for that structure across all patients. The interaction of dose and time will be tested within the model to assess whether dose mediates longitudinal trends. In addition, potential fixed-effect covariates will be selected from a list of patient and tumor-specific variables, such as age, sex, tumor size and location. Model selection will be based on AIC. To account for correlated observations within subjects, patient-specific random intercepts and time-associated slopes will be tested.

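### A one-sample t-test is fixed for two yes/no rates, 6-month local control and 12-month survival: it is lopsided at high control rates, and would mishandle clustered lesions or unknown vital status if either arises

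*Protocol*

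**What the plan says.** The protocol's Primary Objective Analysis (under Statistical Considerations) closes with two supporting comparisons: "Local tumor control rate at 6 months and overall survival rate (death from any cause) at 12 months will be compared to historical values", "using a 1-sample t-test". The method is therefore chosen in the protocol and not left open.

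On the unit of local control, the same section says "Local tumor control of each treated lesion will be assessed with modified RANO criteria", with progression defined by a threshold of more than 25% growth, so each lesion is scored yes or no. The follow-up paragraph after the SRS planning text says "Local tumor control rates for each treated lesion will be assessed". Inclusion criterion 2 admits "One to three brain metastases targets, all smaller than 3 cm in diameter". No sentence says whether the tested rate has lesions or patients as its denominator.

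On follow-up, the Research Plan schedules MRI at baseline "and 1 month, 3 months, and 6 months afterwards", and the follow-up paragraph lists clinical and imaging exams at the same three times. No 12-month contact appears in the visible text; Figure 1, the timeline, is not shown.

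**The concern.** A t-test on 0/1 data is a large-sample approximation. It works tolerably when the rate is near one half, but when most outcomes are successes its two error tails become unequal. Two further features could matter here. If lesions are the unit, up to three of them share a patient, and a plain t-test treats them as independent. For survival, the test needs a known alive-or-dead status at 12 months for everyone, and has no means of using a patient followed for only part of that time.

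These are the only statistical comparisons of tumour control and survival with standard SRS in the visible text. The protocol expects both to be comparable to other SRS-alone studies, and readers will look to these results to judge whether sparing costs tumour control.

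**Working it through.** The protocol gives no historical rate, sample size, power, correlation or loss rate for these two endpoints, so there is no stated figure to reproduce. Taken from the protocol: 60 patients enrolled, n=48 after 20% drop-out (Sample Size Determination, for the 3-month cognitive endpoint), one to three targets per patient. Assumed: two-sided 5% level (stated only for the primary endpoint), historical control of 80-90%, 12-month survival of 40-70%, and the correlations and losses shown.

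**1. Independent yes/no data, n=48, historical control 80%.** For x patients controlled, p = x/48 and t = (p - 0.80) / sqrt(p(1-p)/47), with critical value 2.012.
- x = 43: p = 0.8958, standard error 0.0446, t = 2.15, rejected. P(X >= 43) = 6.2%.
- x = 32: p = 0.6667, standard error 0.0688, t = -1.94, not rejected. x = 31: t = -2.21, rejected. P(X <= 31) = 0.9%.
- The exact binomial test, with at most 2.5% per tail, rejects at x <= 32 (2.1%) and x >= 44 (2.5%).

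The cut-off moves by one patient on each side. At n=60 and 80% the t-test's harm tail is 1.1% against 2.2% exact; at n=60 and 85% the two harm tails are identical (1.36%).

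**2. Lesion-level rate.** Assume 48 patients, of whom 50/30/20% have 1/2/3 lesions. Then E[m] = 0.5 + 0.6 + 0.6 = 1.7 and E[m²] = 0.5 + 1.2 + 1.8 = 3.5. The design effect is 1 + (3.5/1.7 - 1) × correlation, which is 1.11 at a correlation of 0.1. Beta-binomial simulation of the t-test when true control equals the historical rate (harm / favourable tail):

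| Correlation | 80% control | 90% control |
|---|---|---|
| 0 | 1.4 / 4.4% | 1.0 / 5.9% |
| 0.2 | 2.4 / 6.3% | 1.7 / 7.9% |
| 0.4 | 3.4 / 7.5% | 2.4 / 9.8% |

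At a correlation of 0.1 the totals are about 7% (80% control) and 8% (90% control). At 0.2-0.4 they run from about 8% to 12%, varying slightly between simulation runs. With no correlation the total is already 5.8-6.9%, so part of the excess is skewness and not clustering. A patient-clustered interval on the logit scale has a total error of 3.8-4.6% in the same settings.

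**3. Survival at 12 months.** Let S be true survival and L the probability of loss by 12 months, both exponential and independent. Known alive: a = S(1-L). Known dead: d = [ln S / (ln S + ln(1-L))] × (1-a). Dropping unknowns estimates a/(a+d); counting them alive estimates 1-d.

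Example, S = 0.60, L = 0.20: a = 0.48; d = (0.511/0.734) × 0.52 = 0.362; unknown = 1 - 0.48 - 0.362 = 0.158, or 9.5 of 60 patients. Dropped: 0.48/0.842 = 57.0%, a bias of -3.0 points. Counted alive: 63.8%, or +3.8 points.

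Over S = 40-70%:
- L = 5%: -0.6 to -0.7 (dropped), +0.7 to +1.3 (counted alive).
- L = 10-20%: -1.2 to -3.2 (dropped), +1.4 to +5.3 (counted alive).

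The standard error of the rate with 60 patients is 5.9-6.5 points. With complete status, the t-test's tails are 2.0-2.9% each. Under this independent-loss model the Kaplan-Meier estimate is unbiased to within 0.1 point.

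**The case against.** The strongest reply is that much of this is conditional. Assessing each lesion does not fix the denominator of the test. A patient-level yes/no rate removes the clustering, and so does a t-test on each patient's fraction of controlled lesions, which is a natural use of a t-test. This stands: a reader might infer that the planned test ignores clustering, but the text does not settle that.

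A reader might also infer that the lopsided error hides a loss of control. The lesion-level figures do not show that. They assume control equal to the historical rate, so the favourable tail is a false claim of superiority, and the harm tail stays at about 1-3%.

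On survival, a reader might infer that 12-month status will be missing because the listed exams stop at 6 months. Vital status needs no study visit, the protocol commits to a 12-month rate, and the 20% drop-out it states concerns the cognitive endpoint. Loss is therefore an assumption, and with complete status the t-test is adequate.

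Finally, the imaging models in Secondary Objective Analyses are preferred because "they account for within-subject correlation between repeated measures, and allow for incomplete outcome data". That shows the issues were recognised, but those models serve continuous repeated measures, so a different method for two supporting rates is no contradiction.

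What the reply does not remove is that a t-test is fixed for rates it approximates poorly when control is high, and that it offers no route if lesions are pooled or follow-up is incomplete.

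**Conclusion.** The point holds as a minor one, to consider. Lopsided error at control rates near 80-90% arises even with independent data, though it amounts to about one patient in the cut-off. The clustering error applies only if lesions are the unit, and its size depends on the assumed correlation and lesion mix. The survival bias applies only if some 12-month statuses are unknown; at the losses assumed it is smaller than one standard error. Both comparisons are unpowered and supporting, the planning rules protect tumour coverage, and the primary cognitive endpoint is not affected. The documents do not support saying that the trial would conceal harm or that its survival comparison is invalid.

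**What to change.** - **Survival:** replace the t-test with the Kaplan-Meier estimate at 12 months and its 95% confidence interval, set against the historical value, and check vital status in the medical record at 12 months. The estimate still assumes that loss is unrelated to prognosis, which is why the record check matters.
- **Local control:** state whether the unit is the lesion or the patient, matched to the historical figure. For lesions, use a patient-clustered 95% confidence interval on the logit scale; for patients, use an exact binomial interval. The logit interval cannot be computed if every lesion is controlled, so name a fallback. Finer details can sit in the SAP.

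The cost is a change of wording, slightly more analysis work and one chart check per patient. No visits, scans or patients are added. By the protocol's Feasibility text, accrual takes 15-20 months; adding 12 gives 27-32 months, inside the four-year (48-month) grant period.

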Computers containing access to protected health information will have password-access; and screen-savers will be utilized to prevent unauthorized viewers from inadvertently seeing information. Protected health information will be stored on secure servers. The servers supporting these studies are located inside a locked rack within the San Diego Supercomputer data center. The facility features restricted access by means of personal codes (PINs) and biometrics, and is monitored 24 hours a day 7 days a week. The electrical power is backed up by battery-powered uninterruptible power supplies, as well as by on-site generators. Both servers are behind firewalls configured to allow access only to credentialed personnel within the UCSD network. Velos, the clinical

trials management system, maintains an additional internal access control mechanism via user names and passwords. Data transactions executed over our intranet are encrypted via Secure Sockets Layer.

Access to a subject's protected health information will be limited to those study personnel who need to use it to accomplish the purpose of the research, and the minimum necessary information to accomplish the purpose of the research will be collected, stored, used, and reported. When protected health information is sent outside the University of California, San Diego, it will be disclosed only to those parties listed in the subject's authorization, and an audit trail log will be maintained of what information was sent and to whom it was sent.

Patients will be assigned a random study identification number for purposes of organizing the data and the data for the study will be kept in 2 main files: the "central" file and the "code" file. After the data is collected, it will be stored in the "central" file (that will contain no patient-identifying information such as name, date of birth, MRN, etc.). A separate, password-protected "code" file will contain the mappings of patient name with their random study identification number. This file will be password-protected, with the password known only to CITI-trained study personnel, and it will be stored exclusively on the computer of the principal investigator. These patient identifiers will be destroyed following the collection and aggregation of the dataset, and thus the patient data will be officially de-identified at this time.

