Subject identifiers will be destroyed by the PI at the earliest opportunity consistent with the conduct of the research, unless there is a health or research justification for retaining the identifiers or such retention is required by law.

6. Data Safety and Monitoring

Personnel responsible for the safety review and its frequency

The principal investigator will be responsible for monitoring the data, assuring protocol compliance, and conducting the safety reviews at the specified frequency which must be conducted at a minimum of every 6 months (including when re-approval of the protocol is sought). During the review process, the principal investigator will evaluate whether the study should continue unchanged, require modification/amendment, continue or close to enrollment. The principal investigator has the authority to stop or suspend the study or require modifications. This study has been approved by the UCSD Institutional Review Board.

Attribution of Adverse Events

Adverse events will be monitored for each subject participating in the study and attributed to the study procedures by the principal investigator according to the following categories:

Definite: Adverse event is clearly related to investigational procedures

Probable: Adverse event is likely related to investigational procedures

Possible: Adverse event may be related to investigational procedures

Unlikely: Adverse event is likely not to be related to the investigational procedures
Unrelated: Adverse event is clearly not related to investigational procedures

Plan for Grading Adverse Events

Adverse events noted during the study will be graded using the NIH Common Toxicity Criteria for Adverse Events scale (CTC), version 4.0 (<http://evs.nci.nih.gov/ftp1/CTCAE/About.html>). Specific conditions and symptoms may have values or descriptive comment for each level, but the general guideline is:

1 - Mild

2 - Moderate

3 - Severe

4 - Life threatening

5 - Death

Plan for Determining Seriousness of Adverse Events

In addition to grading the adverse event, the PI will determine whether the adverse event meets the criteria for a Serious Adverse Event (SAE). An adverse event is considered serious if it:

1. Is life-threatening

2. Results in in-patient hospitalization or prolongation of existing hospitalization
3. Results in persistent or significant disability or incapacity
4. Results in a congenital anomaly or birth defect
5. Results in death

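### Overall survival is to be compared with history at 12 months, but the described follow-up ends at 6 months and no procedure for later vital status is given

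*Protocol*

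**What the plan says.** In section 3, Statistical Considerations, Primary Objective Analysis, the protocol expects local control and survival to be similar to those in other SRS-alone studies. It plans two historical comparisons: local control at 6 months, and survival, where "overall survival rate (death from any cause) at 12 months will be compared to historical values". Both are to be made "using a 1-sample t-test". No rule is given for patients whose status at 12 months is unknown.

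The follow-up is described in three places:

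- The opening of section 3 schedules MRI "at baseline (pre-SRS), and 1 month, 3 months, and 6 months afterwards".
- The same paragraph limits cognitive testing: "Formal neurocognitive assessments will be performed at baseline and 3 months post-SRS".
- The text on SRS planning and treatment has patients "followed closely with clinical and imaging exams for safety and tumor recurrence (i.e., 1 month, 3 months, 6 months post-SRS").

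Section 5, Privacy and Confidentiality, covers the file linking study numbers to patients. It says "These patient identifiers will be destroyed following the collection and aggregation of the dataset", and later "Subject identifiers will be destroyed by the PI at the earliest opportunity consistent with the conduct of the research", with an exception where there is a health, research or legal reason to keep them.

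**The concern.** The survival outcome sits 6 months beyond the last contact described. Local control shows the contrast: it is assessed at 3 and 6 months and compared at 6, so its time point matches the schedule. Survival is the one named outcome with no assessment to match.

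This is more than a detail for an analysis plan. An analysis plan can say how to handle missing status, but whether status is sought at all is settled by the protocol's schedule. The named test also leaves no room for incomplete follow-up. A 1-sample t-test on a yes/no survival status needs a known value for every patient at 12 months and does not handle censoring.

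At stake is the credibility of a supporting claim. The trial has no concurrent control arm, and the protocol concedes that changing the plan to spare cognitive structures may alter dose elsewhere in the brain, with unclear effect on clinical outcomes. Because eligibility requires an expected survival above 6 months, many deaths can be expected after the described window closes.

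**Working it through.** **1. Time points side by side**

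| Item | Last time described | Where |
|---|---|---|
| Cognitive testing | 3 months | Section 3, opening |
| MRI | 6 months | Section 3, opening |
| Clinical and imaging exams | 6 months | Section 3, SRS planning and treatment |
| Local control comparison | 6 months | Primary Objective Analysis |
| Survival comparison | 12 months | Primary Objective Analysis |

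Gap: 12 − 6 = 6 months with no described means of learning vital status.

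**2. Incomplete status is likely without a procedure.** Sample Size Determination assumes 20% drop-out: 60 × 0.80 = 48, so the protocol itself plans for 12 patients without the 3-month outcome. Their status at 12 months is not secured by any scheduled contact.

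**3. Size if patients last seen at 6 months are counted as alive.** The protocol prints no survival figure, so these inputs are assumptions. With exponential survival S(t) = 0.5^(t/median), the overstatement is S(6) − S(12), and the deaths missed are 60 times that.

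| Assumed median (months) | S(6) | S(12) | Difference | Deaths missed of 60 |
|---|---|---|---|---|
| 8 | 0.595 | 0.354 | 0.241 | 14.5 |
| 12 | 0.707 | 0.500 | 0.207 | 12.4 |
| 18 | 0.794 | 0.630 | 0.164 | 9.8 |

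This gives 16 to 24 percentage points.

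**4. The same quantity without the exponential form.** Assume 6-month survival of 60-90%, and survival from month 6 to month 12 among those alive at 6 of 70-90%. The overstatement is S(6) × (1 − conditional survival).

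- Smallest: 0.60 × 0.10 = 0.06, or 3.6 deaths of 60.
- Largest: 0.90 × 0.30 = 0.27, or 16.2 deaths of 60.

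This gives 6 to 27 points. Both calculations suppose that no death after month 6 is found.

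**5. Does a 12-month check fit the timeline?** The Feasibility paragraph gives 60 patients at 3-4 per month. 60/4 = 15 and 60/3 = 20 months, which reproduces the stated 15-20. The last patient reaches 12 months at 15 + 12 = 27 to 20 + 12 = 32 months. The same paragraph also speaks of accrual over 3 years, which gives 36 + 12 = 48 months, the whole four-year grant period.

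**The case against.** The strongest reply is that the protocol is silent here rather than wrong. Date of death needs no exam, this is a single-institution study whose staff review medical records, and naming a 12-month survival outcome implies that someone will obtain it. That is partly right. A reader might infer that deaths between months 6 and 12 will not be collected, and the document does not support so strong a statement. It supports only that no procedure for collecting them is described. The gap remains, because record review is nowhere required for this purpose and would miss patients who leave the institution's care.

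A reader might also infer that identifiers are destroyed once the 6-month visits are over, making later ascertainment impossible. Section 5 does not say that. It gives no month, ties destruction to the completed dataset and the needs of the research, and allows retention for a research reason. Twelve-month survival can be read as part of that dataset. The only fair remark is that nothing expressly ties the code file to the 12-month status.

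Three further points stand:

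- The list of exam times should not be called closed merely because it is introduced by an abbreviation that this protocol also uses for examples. The MRI schedule ends at 6 months independently of it.
- Figure 1, the patient timeline, was not visible for this review. A 12-month entry there cannot be excluded, though the text gives no sign of one.
- The 16 to 24 points follow from a counting rule that the protocol does not contain. The 8-month median implies 41% dead by month 6 (1 − 0.595), which fits poorly with the life-expectancy criterion.

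Finally, survival is neither a stated objective nor the powered endpoint, and adverse events are recorded and reviewed separately.

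**Conclusion.** The point holds in this form: the protocol commits to a 12-month survival comparison by a test that needs complete status, while its described follow-up ends at 6 months and gives no means of establishing vital status afterwards. The schedule therefore does not support the stated time point.

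If status is incomplete, bias is probable and upward is the likelier direction. Carrying patients last seen at 6 months as alive overstates survival with certainty whenever any of them has died. Using only those with later records probably does so too, since surviving patients are the ones who return, although selective recording of deaths could pull the other way.

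The size cannot be fixed from the document. For illustration, it is up to about 16 to 24 points with exponential survival, medians of 8 to 18 months and no later deaths found, or 6 to 27 points under the looser assumptions above. If record review finds most deaths, the bias would be much smaller.

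The 3-month cognitive endpoint is unaffected. This should be corrected, but it does not threaten the main result.

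**What to change.** Either of two changes reconciles the text.

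1. **Keep 12 months.** In the opening of section 3 and in the follow-up text under SRS planning and treatment, add a vital-status check 12 months after SRS for every enrolled patient, including those who dropped out. Record the date of death or the date last known alive, by record review or telephone. In section 5, state that the code file is kept until the last patient's 12-month status is entered. If some patients are still lost before 12 months, a Kaplan-Meier estimate at 12 months with a confidence interval, set against the historical value, would use their partial follow-up, which the t-test cannot.
2. **Move the comparison to 6 months**, so that it matches the described follow-up. The historical value must then be taken at 6 months too.

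If Figure 1 already shows a 12-month contact, bring the text into line with it.

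The first option costs one record check or call per patient and a longer-held identifier link, with no added visit or scan. At the expected accrual of 15-20 months, the last check falls at study month 27-32, well inside the grant. At 3 years' accrual it falls at month 48 and leaves no time for analysis, so the accrual plan should be settled at the same time. The second option costs nothing in data collection but gives up any view of survival after 6 months.
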